## **E. Informed Consent Process**

Informed consent for Procedure 1 and Procedure 2 will be collected electronically. Individuals will consent to participate at the beginning of the survey by clicking that they consent to participate after reading the consent form and by typing their name and the date "(type name and date: \_\_\_\_\_)". They will also complete a consent quiz to check for understanding. Incorrect answers will be followed up with the correct answer and then participants will be permitted to proceed. Participants will be provided a copy of the informed consent using the same process they select for receiving payment (email, mail, or in-person).

This research will not involve minors or individuals of diminished capacity given the requirements of treatment centers. The research was designed the research to only solicit anonymous information about children from the fathers to avoid having to engage children in the research.

We are requesting a waiver of documentation of informed consent. The research presents no more than minimal risk of harm to subjects and involves no procedures for which written consent is normally required outside of the research context.

There will not be any deception.

The investigators will post a copy of the consent form as required and will use the study's established registration at clinicaltrials.gov to post the document within the required timeframe.

## **F. Provisions for Participant Privacy and Data Confidentiality**

### **1. Privacy**

During the intervention, it will be up to participants to disclose vulnerable information about their previous experiences with parenting. It will be their choice to disclose such information during coaching calls however, in services as usual, they would disclose similar parenting information.

To promote protection of privacy \ during coaching calls there will be a designated time decided on by the participant when the coach will call. The coach will not disclose that the participant is a research study when the call is made in case someone else answers the participant's phone.

Regarding privacy protections for mailing payments to Procedure 2 participants, return envelopes will be labeled with "University of Oregon Prevention Science Institute" without a reference to the study and in the check note, "CPO Pilot 2". The envelopes and checks issued for payments will not include the study title nor other information on outward facing materials that would indicate the participant is in recovery.

### **2. Data Disposition**

Identifiable participant information will be collected in Qualtrics or RedCap during each survey. Following data collection, identifiable data will be removed, and a unique identifier assigned for all analyses. The clinician will only be given the participants first name and phone number to maintain confidentiality.

### **3. Confidentiality**

The only individuals with access to identifiable participant information on Qualtrics or RedCap will be the PI and advisor. The code and key will be retained in a locked file on the Prevention Science Institute (at University of Oregon) server with permissions granted to only [name] and [name].

Participant identities will not be disclosed as a result of this research.

Storage of data will be stored electronically on a private server and will be directly uploaded only while using secure wifi. If the data must be transferred, they will be transferred using a secure client server. Only the PI and advisor will have access to the data. Students may be granted access to the data after signing a data use agreement, in order to complete analyses. Records will be kept for up to 3 years after the study has been completed.

Participants will be informed that researchers are mandatory reporters and are required by law to report a situation if they have reasonable cause to believe that any person with whom they come into contact has abused a child.

Research funded by NIH automatically has a Certificate of Confidentiality associated with it. This is added protection against forced disclosure of research information in circumstances of subpoena.

### **Sharing data**

This research study is part of a larger set of related studies being conducted by the Center on Parenting and Opioids (CPO; cpo.uoregon.edu), a National Center co-located at UO's Prevention Science Institute (PSI), UO's Center for Translational Neuroscience (CTN) and Oregon Health and Sciences University (OHSU). The research at CPO is funded by an award from the National Institute on Drug Abuse (NIDA).

De-identified data collected as part of the current protocol will be shared to a central data repository maintained by CPO. The repository will house de-identified data collected from all research projects within CPO. Data will be coded with a unique identifier that cannot be linked to any identifiable information. The repository is encrypted, and password protected behind firewalls. This expectation for data sharing is in accordance with guidelines from national funding agencies (e.g., see NIH Data Sharing Policy here:

[http://grants.nih.gov/grants/policy/data\\_sharing/index.htm](http://grants.nih.gov/grants/policy/data_sharing/index.htm)). Therefore, we will ask participants to consent to sharing their de-identified data to the data repository created and managed by CPO.

#### **G. Potential Research Risks or Discomforts to Participants**

Information risks, psychological risks, and social risks may occur as the result of participating in this study. Information risks include loss of privacy and/or breach of confidentiality. Since data will be collected using only private wifi (except when participants are not connected to secure wifi) and will be stored on a secure server, it is unlikely that loss of privacy will occur. A breach of confidentiality may occur if the clinician discloses identifiable participant information. The clinician will be asked to sign a confidentiality agreement before providing services.

Psychological risks may occur such as guilt or loss of self-esteem while receiving or not receiving parenting intervention services. It is likely that both the treatment as usual and the treatment conditions will improve fathers' sense of responsibility without inducing guilt and improve self-esteem but not everyone receives treatment uniformly. Participants will be encouraged to seek services if they are in need of additional support. The clinician will be responsible for providing these resources as part of the services they provide to the study.

Social risks may occur as a result of receiving services in the participant's home (i.e. watching videos and phone coaching calls- no one will physically be in the participant's home). Specifically, participants might feel uncomfortable engaging in the intervention if they do not have a private space to participate.

All risks will be communicated in the informed consent process.

The protocol involves intervention. The intervention includes watching videos that have been used for prior research studies with divorced and separated fathers. It also includes on-on-one parenting coaching with a clinician who is a trained clinician. This research does not pose any additional risk over the services provided as usual since fathers in treatment also receive services aimed at improving parenting via phone as part of standard practice at treatment centers (not as part of the proposed intervention).

The funding agency required a Data Safety Monitoring Plan for this research at the time of funding proposal. A copy of the DSMP submitted to the funder is attached; however, it should be noted that there are some discrepancies due to the evolution of the project following proposal. The discrepancies are documented in a separate Memo to File. The key differences are that no information is being obtained from the treatment facilities, and the research no longer plans to include families and children as subjects. We are no longer excluding fathers of children with a developmental disability since children are not research subjects. Only fathers will participate. Additionally, our sample size is now 120 instead of 80. There will be three points of data collection rather than two. All other key components of the DSMP as proposed persist including the defined roles and responsibilities, procedures for monitoring site performance, procedures for monitoring data integrity, protecting confidentiality, and safety reporting and monitoring. Additionally, in the event of a crisis such as expressed elevated suicidality or intent to harm self or other, [name], who is currently receiving supervision to obtain licensure, will create a safety plan with the client (attached) and will make a referral to the appropriate agency such as the emergency department, back to the treatment center they are receiving services from if the client is currently receiving services, a local therapy center such as Options Counseling, or Child Welfare if warranted.

There is no established Data and Safety Monitoring Board/Committee (DSMB/C) as noted in the DSMP.

#### **H. Potential Benefits of the Research**

Individuals may receive benefits from participating in this research such as improvements in parenting skills and the opportunity to form relationships with other fathers who might have experienced similar situations.

As a result, relationships between the participant and his child may improve as well as the relationship between the participant and the child's other parent.

By participating in this research, the research team will be able to learn whether the intervention would be generally useful for fathers receiving drug and alcohol treatment.

### **2. Roles and Research Duties**

The PI or research assistance will consent participants and administer on-line surveys. The clinician will deliver the intervention.

The PI and faculty advisor will be responsible for data management, reporting, and science communication. The PI and faculty advisor will also be responsible for documenting program changes.

### **3. Training and Oversight**

The clinician, [name] has previous experience conducting similar parenting coaching intervention to those being used for this study. There is no certification for delivering the intervention however, on previous studies, [name] has demonstrated high adherence to the intervention principles. Training may be provided to graduate student research assistants or treatment center personnel by the clinician. If any trainees are used, they will be added to the protocol and will be part of the calls/delivery of the clinician coaching and will receive clinical supervision by their University department.

Graduate student research assistants will complete CITI training, and will be supervised by the PI. They will be responsible for delivering the text message script and will review PI-participant text messaging records for training. The PI will review all text exchanges to ensure there are no ethical concerns and to provide feedback.

**12132019.029**

**A Substance Use Adaptation of Fathering Through Change**

**March 19, 2023**

## Statistical Analysis Plan

Primary outcome hypotheses were tested using standard normal autoregressive, analysis of covariance, models. More specifically, the post-intervention follow-ups were estimated as random intercept models for the 6-week and 4-month follow-ups. For the secondary outcome of substance use count of days or count of use status as a binary outcome, generalized linear models were estimated. Given the small sample size and two waves of repeated measures for the random intercept, models were estimated using robust standard errors to address nonindependence. Evaluation of the 5 primary outcomes were corrected for false discovery rate (Benjamini & Hochberg, 1995). Missing data patterns were evaluated to assess random missingness. with Little's MCAR test (Little, 1988). Little's MCAR test revealed that the data were missing completely at random and the estimated means and covariances for partial data fathers was not significantly different than fathers' with complete data ( $\chi^2(168) = 193.99$   $p = .083$ ).

Benjamini, Y., & Hochberg, Y. (1995). Controlling the False Discovery Rate: A Practical and Powerful Approach to Multiple Testing. *Journal of the Royal Statistical Society. Series B, Methodological*, 57(1), 289-300. doi:10.1111/j.2517-6161.1995.tb02031.x

Little, R. J. A. (1988). A test of missing completely at random for multivariate data with missing values. *Journal of the American Statistical Association*, 83(404), 1198-1202.

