#### **D. Research Population & Recruitment Methods**

**Procedure 1 (Intervention Study):** The participant population are fathers who are in recovery from substance use disorders and have been abstinent from illicit substances for less than 18 months. Participants must be over the age of 18 years old. Our primary intervention target is fathers with opioid use disorder and efforts will be made to prioritize fathers who have specifically misused opioids in the past.

Fathers are eligible to participate if:

1. They identify as being in recovery and have been abstinent from illicit substances for at least 1 day and less than 18 months.
2. They have parenting responsibilities for a child between the ages of 3-16 who they spend at least 2 hours per week with.
3. They speak English.
4. They are 18 and older.

The project coordinator will complete the eligibility screener via text message or phone call. Individuals will be asked to describe their recovery and family situation to the project coordinator through open ended questions. Individuals will be excluded if they do not meet eligibility criteria, or if they deny answering questions about their recovery and family situation. Individuals will be excluded if they cannot speak English because they will not be able to understand intervention content and will not be able to participate in surveys. Father's must have potential to have some contact following treatment since the intervention is targeted at improving parenting skills. Fathers of children younger than 3 or older than 16 will be excluded because the intervention is not suitable for children outside of the age range 3-16.

The total number of participants will not exceed 80 for procedure 1. Our goal is to recruit approximately 40 fathers to the intervention condition and 40 fathers to the control condition. This will provide enough data to compare effectiveness between condition and also to examine the effects of different substances on intervention outcomes. We expect these numbers may be less due to COVID-19.

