The total number of participants will not exceed 120 for the baseline only survey. This number includes the participants who also participated in procedure 1 so we would recruit 120-number recruited for procedure 1. We anticipate that recruitment is finished for procedure 1 and we have enrolled only 41 subjects, thus, we expect that no more than 79 participants will be recruited for the baseline only survey.

Similar procedures for virtual recruitment from procedure 1 will be followed in the event of virtual recruitment for procedure 2. For procedure 2, the project team may travel to treatment centers to complete the eligibility screener and offer the chance to complete the survey in person via an iPad. Treatment centers will allow the research team to be present on site, and will provide an indoor or outdoor space that allow for sufficient spacing and privacy to mitigate risks associated with COVID-19 transmission and loss of privacy. The treatment centers will let fathers know that the study team is on site and fathers will voluntarily approach the study team in a location where the study team is not able to see treatment center attendees to mitigate HIPAA privacy concerns. We will work with treatment centers who consent to in-person recruitment to determine the best process to talk with clients while on site. This might vary based on the type of treatment center. For example, the Methadone clinic has people coming and going regularly, thus

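### If one arm reports no substance use, the Wald test from the SAP's generalized linear models is uninformative, and with robust standard errors a single user in the other arm can look overwhelmingly significant

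*SAP*

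**What the plan says.** The SAP's single analysis section deals with substance use in one sentence: "For the secondary outcome of substance use count of days or count of use status as a binary outcome, generalized linear models were estimated". It does not state the link, the distribution for the day count, the test statistic, or what happens if few fathers or none in an arm report use. The next sentence reads "Given the small sample size and two waves of repeated measures for the random intercept, models were estimated using robust standard errors", with nonindependence as the purpose. The repeated measures come from "random intercept models for the 6-week and 4-month follow-ups", a phrase used for the primary outcomes. The false discovery rate correction is stated for the five primary outcomes only. The Analysis Plan paragraph in Protocol section C does not describe a model for substance use.

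On numbers, Protocol section D states the aim as "Our goal is to recruit approximately 40 fathers to the intervention condition and 40 fathers to the control condition". Under Procedure 2 it then says "We anticipate that recruitment is finished for procedure 1 and we have enrolled only 41 subjects". Fathers qualify for Procedure 1 if they have been "abstinent from illicit substances for at least 1 day and less than 18 months".

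**The concern.** With about 20 fathers per arm, all abstinent from illicit substances for at least a day at entry, one arm could have no users at follow-up. That is separation: in a logistic or log-link model the arm coefficient has no finite maximum likelihood estimate. A Wald test divides that runaway coefficient by a standard error, so the answer depends on how the standard error behaves. The model-based one explodes with the coefficient. The sandwich one does not.

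Substance use is the only secondary outcome the SAP names. In fathers in recovery, a statement that the programme abolished or provoked use would carry weight. The stated method could produce it, in either direction, from one or two men.

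**Working it through.** The plan gives no figure for this outcome, so there is none to reproduce.

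**Inputs from the documents.** 41 fathers enrolled in Procedure 1 (Protocol section D); two follow-up waves and robust standard errors (SAP).

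**Assumptions.** A 20 v 21 split; logit link for any use and log-Poisson for days; Wald tests at two-sided 0.05; sandwich errors clustered on father; the use rates shown below.

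**1. Why the robust standard error stays small.** Take one user, at both waves, in the arm of 20, and none in the arm of 21.
- User arm: fitted p = 1/20, and the sandwich variance of its log odds is 1/(20 × 0.05 × 0.95) = 1.053.
- Empty arm: suppose the fitted probability has reached a tiny value e when fitting stops. Each of the 21 fathers contributes a score of -2e, and the information is about 2 × 21 × e. The sandwich variance is 21 × 4e² / (42e)² = 1/21 = 0.048, whatever e is. The model-based variance is 1/(42e), which grows without limit.
- So the robust standard error of the arm effect is at most about √(1.053 + 0.048) = 1.05, while the coefficient keeps growing.

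**2. Fitted results for that data set.**
- Any use, robust: coefficient 20.6, standard error 1.05, z = 20.6/1.05, about 20.
- Five days of use per wave, log-Poisson, robust: coefficient 22.4, standard error 0.99, z about 23.
- Model-based Wald p: 0.999 for both.
- The robust p has no meaningful size. For any use it is about 1e-27, 4e-54, 1e-86 and 1e-189 at convergence tolerances of 1e-4, 1e-6, 1e-8 and 1e-12. All that can be said is that it is near 0.
- Bias-reduced robust errors, HC3 errors, and adding wave and a baseline covariate did not help. In a parallel run with one user in each arm, at one wave, the robust p was 0.97, so the empty arm is the cause.

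**3. Exact comparison.** With one user, Fisher's p is 20/41 = 0.49 if he is in the arm of 20, and 20/41 + 21/41 = 1.00 if he is in the arm of 21. With two users and none opposite it is 0.23 or 0.49; with three, 0.11 or 0.23. Firth-penalised logistic regression on one record per father gives p = 0.48 or 0.52 for the single user.

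**4. How often one arm is empty by chance.** With one record per father and equal true rates r, P = a(1 - b) + b(1 - a), where a = (1 - r)^20 and b = (1 - r)^21.
- r = 5%: a = 0.358, b = 0.341, P = 45%
- r = 10%: a = 0.122, b = 0.109, P = 20%
- r = 15%: a = 0.039, b = 0.033, P = 7%
- r = 20%: a = 0.012, b = 0.009, P = 2%
- r = 30%: P = 0.14%

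**5. Simulated false-positive rate.** Two waves, no true effect, agreement between waves 0.3 to 0.8, skewed days among users. Ranges span settings and repeat runs.

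| Assumed use per wave | Any use | Days of use |
|---|---|---|
| 5% | 28-42% | 37-46% |
| 10% | 7-16% | 16-22% |
| 15% | 4-7% | 10-12% |
| 20% | about 5% | 8% |
| 30-40% | about 5-6% | 6-7% |

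The rates at 5% lie at or below the 45% in step 4 for any use because an arm must be empty at both waves. Day counts also over-reject without an empty arm, because a few heavy users drive the mean ratio.

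**The case against.** The strongest reply is that the trigger is not in the documents. Eligibility asks for as little as one day without illicit substances, and the SAP does not limit its outcome to illicit substances, so use may have been common. At 20% or more, the binary test holds its level and the day-count test is only mildly liberal. This stands, and it confines the point to sparse data.

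Second, the robust-error sentence gives the random intercept as part of its reason, and that intercept is described for the primary outcomes. Applying it to the substance use models is likely, since the sentence follows directly and speaks of models generally, but it is not certain. If model-based errors were used, the failure reverses: p near 1, whatever the data show. The Wald test would still be uninformative.

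Third, 41 is an enrolment count given when recruitment was expected to be over. Protocol section C allows baseline-survey fathers to be re-contacted for possible enrolment, and no analysed number is given. This also stands but matters little: the robust test failed in the same way at every split tried from 12 v 12 to 40 v 40.

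Fourth, the SAP is written in the past tense, so the counts of users already exist. A reader might infer that the trial's substance use result is therefore a false positive. The documents do not support that: they report no use by arm and no result for this outcome.

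**Conclusion.** The point holds conditionally. If the link is logit or log, the tests are Wald tests and one arm has no users, the stated method cannot give a usable p-value: near 0 with robust errors, near 1 with model-based errors, against an exact p of 0.49 or 1.00 for a single user. How likely this was depends on a use rate the documents do not give. The false-positive rate ranges from roughly 28-46% at 5% use per wave to close to nominal at 20% or more.

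It would be wrong to conclude that the error rate in this trial was as high as the upper figures, since they belong only to the lowest rate simulated. For a secondary outcome this is a change worth making because it is cheap, not a flaw that undermines the trial.

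**What to change.** - Report the number of users and the days of use, by arm and wave. If neither arm is empty or nearly so, this largely settles the matter for any use.
- State the link, the distribution and the test.
- Test the arm difference with a father-level permutation test that follows the allocation actually used. The protocol says assignment was made in batches of 10 but not that each batch was balanced, so this must be checked first. Fisher's exact test on any use is the simple alternative.
- If a model estimate is wanted, use Firth-penalised logistic regression on one record per father, with profile-likelihood intervals.
- Report no Wald p-value when an arm has no users.

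A likelihood ratio test alone does not repair the Poisson model. With 20 v 20 fathers and one man using on five days, the statistic is 2 × 5 × ln 2 = 6.93, p = 0.008, because overdispersion is ignored.

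The cost is a short SAP addition and a re-run on existing data. The exact test is conservative: with one record per father, Fisher's true size is 0.7% at 5% use, 2.5% at 10% and about 3.5% at 20%. It also gives up baseline adjustment.

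### The substance use outcome may be tested in either of two forms outside the multiplicity correction: an error rate of about 7–10% if either can count, and more if the count model over-rejects in a small sample

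*SAP*

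**What the plan says.** The SAP (Statistical Analysis Plan) describes the substance use analysis in one sentence: "For the secondary outcome of substance use count of days or count of use status as a binary outcome, generalized linear models were estimated". It does not say which form carries the test or whether both are reported.

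The correction is limited in scope: "Evaluation of the 5 primary outcomes were corrected for false discovery rate". The secondary outcome is not mentioned there.

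On time points, the SAP says that "the post-intervention follow-ups were estimated as random intercept models for the 6-week and 4-month follow-ups". It does not say whether substance use gets one test over both waves or one at each. On inference, "models were estimated using robust standard errors to address nonindependence", with the small sample given as part of the reason. The count distribution and the type of robust error are not named.

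The Protocol does not fill these gaps. The Analysis Plan paragraph in section C lists families of methods but neither defines the substance use outcome nor mentions a correction. Section D admits fathers who are "abstinent from illicit substances for at least 1 day and less than 18 months" and reports for Procedure 1 that "we have enrolled only 41 subjects". Neither document states a significance level.

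**The concern.** Days of use and any use come from the same answers but can give different p-values. If the analyst may report whichever is favourable, the outcome has two chances at significance and nothing in the plan adjusts for that.

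The days form has a second weakness. Fathers abstinent at entry are likely to give many zeros and a few large counts. Robust standard errors rely on a large sample, and with about 20 fathers per arm a handful of large counts can make them too small. The count test may then reject too often even when it is the only test made.

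At stake is a claim that a parenting programme reduced substance use. That claim would draw attention in this population even though the outcome is secondary.

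**Working it through.** **Inputs.** Two forms, two post-baseline waves and a correction covering five primary outcomes only (SAP). 41 fathers enrolled in Procedure 1, against a cap of 80 for that procedure (Protocol, section D); the SAP gives no analysed number. Assumed, because the documents are silent: two-sided 0.05 per test, the correlation between the two test statistics, the proportion with any use, and the skew of days. The plan states no error rate or power for this outcome, so it offers no figure to reproduce.

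**Step 1: two forms, each a valid 5% test.**
- Independent: 1 − (1 − 0.05)² = 1 − 0.9025 = 9.75%.
- Any dependence: at most 0.05 + 0.05 = 10%.
- Positively correlated z-tests, simulated:

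| Correlation | 0.3 | 0.5 | 0.7 | 0.8 | 0.9 |
|---|---|---|---|---|---|
| Either significant | 9.5% | 9.1% | 8.4% | 7.8% | 7.1% |

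Under the distribution used in step 2, days and any use correlate at 0.66, 0.59 and 0.50 when 30%, 50% and 70% of fathers have any use. If the test statistics correlate similarly, the rate is about 8.4–9.1%.

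**Step 2: the size of the count test itself.** Simulation with no true effect, one wave, no baseline covariate, zero-inflated negative binomial days capped at 30, and robust Poisson and robust logistic models, 3,000 replicates per row. HC0 is the uncorrected robust error; HC1 has a simple degrees-of-freedom correction.

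| n | Any use | Error type | Days | Yes/no | Either |
|---|---|---|---|---|---|
| 41 | 30% | HC0 | 11.7% | 5.1% | 14.5% |
| 41 | 30% | HC1 | 9.9% | 4.9% | 12.7% |
| 41 | 50% | HC0 | 8.6% | 6.7% | 13.4% |
| 41 | 50% | HC1 | 8.1% | 6.0% | 12.4% |
| 80 | 30% | HC0 | 7.9% | 4.6% | 10.9% |
| 80 | 30% | HC1 | 8.7% | 4.9% | 11.9% |
| 80 | 50% | HC0 | 6.3% | 6.1% | 11.0% |
| 80 | 50% | HC1 | 6.5% | 5.6% | 10.8% |

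The Monte Carlo standard error at 12% is √(0.12 × 0.88 / 3000) = 0.6 percentage points.

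Other assumptions at n = 41 move the result:
- One wave, any use 25/40/60%: days 12.3/10.1/7.6%, yes/no 3.6/5.0/7.3%, either 14.6/13.4/12.9%. A repeat gave either-form rates of 14.3/10.8/12.2%.
- Two waves pooled: robust Poisson alone 6–9%, either form 9–12%.
- One wave, skew varied: either form 9–17%, the top arising under heavy skew.
- One wave, HC3 errors (a stronger small-sample correction) with a t reference: either form 8–13%; at the mildest skew the count test alone is 4.6–5.5%, which is nominal.

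**Step 3: separating the two causes.** The either-form rate cannot exceed the sum of the two separate rates. In the first row that bound is 11.7 + 5.1 = 16.8%, and 14.5% was observed. With both tests at 5% the bound is 10%. Anything above 10% therefore comes from a test that is not really at 5%, here mainly the count model.

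**Step 4: what a correction achieves.** With two valid independent tests, Holm gives 1 − 0.975² = 4.94%. Benjamini-Hochberg gives 4.94% + (0.05 − 0.025)² = 4.94% + 0.06% = 5.0%. With the robust Poisson p-value left as it is, Benjamini-Hochberg over both forms still rejects 9.4/8.2/7.0% (any use 25/40/60%). A re-randomisation test on mean days within batches of ten rejects 4.2/4.7/4.2%. Both repairs are needed if both forms are tested.

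**The case against.** The sentence need not license a choice. It can mean that the type of model follows the type of variable, or that both forms were fitted and reported. No success rule for substance use appears in either document. The study is a pilot asking whether the intervention looks promising, and leaving a secondary outcome uncorrected is common. The count-model inflation depends on a Poisson model and an uncorrected robust error, neither of which the SAP names, and it largely disappears under mild skew with better standard errors.

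All of this stands as a limit on size and weight. It does not remove the gap: no text fixes the form, the wave or the count method.

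A reader might go further in four ways that the documents do not support:
- **That two chances alone give 13–15%.** Two valid 5% tests cannot exceed 10%; the excess is small-sample error under assumed distributions.
- **That four tests were made, two forms at each of two waves.** Independence would give 1 − 0.95⁴ = 18.5%, and the correlations tried gave about 12–18%. But the SAP describes models spanning both follow-ups and does not mention separate tests by wave.
- **That the form was chosen after seeing the results.** The SAP is in the past tense and already reports the outcome of Little's test, so the order cannot be established. That leaves selection possible, not shown.
- **That substance use is the outcome of greatest clinical weight.** The documents do not rank it so, and the intervention is aimed at parenting.

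**Conclusion.** The point holds in a limited form. The form of the substance use outcome is open and lies outside the correction. If either form can count as positive at an assumed two-sided 0.05, the error rate is about 7–10%, with 10% the ceiling.

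Separately, at about 41 fathers with many zeros, a robust Poisson-type test can reject about 6–12% on its own, giving roughly 9–15% for either form; some heavy-skew, single-wave settings went a little higher. This second range depends on use rates, skew, number of waves and error type that the documents do not give. The yes/no model, at about 4–7%, shows no material problem.

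This is more than missing detail, because an analysis that follows the sentence as written can carry an inflated error rate. The false discovery rate claim for the five primary outcomes is not touched.

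**What to change.** 1. Report both forms, each pooled over the 6-week and 4-month waves, as one Benjamini-Hochberg or Holm family of two.
2. Name the count model and the type of robust error. Take the p-value for days of use from a small-sample method. If the within-batch allocation is known, re-randomise within the batches of ten, using the same baseline-adjusted statistic as the reported estimate so that p-value and interval do not conflict. The Protocol (section C, step 5) mentions the batches but not the split within each, so the allocation list is needed. Otherwise use small-sample-corrected robust errors with a t reference, accepting that some inflation may remain under heavy skew.
3. As an alternative to step 1, make one form the sole test only if dated records show it was chosen before the data were seen. Give the other as an estimate with an interval and no claim.
4. If no such record exists, label the substance use result exploratory. Data were already in hand when the SAP was written, so a form named now cannot be presented as pre-specified.

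The cost is a few lines of SAP text and code, retrieval of the allocation list, and probably a less favourable p-value on one secondary outcome.
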